1. BACKGROUND AND RATIONALE

Management of cancer is a complex process which involves numerous specialists and stakeholders. In view of this, institutions worldwide have adopted the use of Multidisciplinary Team Meeting (MDTM) for decision of cancer care. By tapping on the collective specialized knowledge and experience of various specialties, MDTM have been shown to result in more accurate staging, more appropriate recommendations and improved patient outcomes [1-2]. At our institution, cancer cases are similarly discussed at regular MDTM which comprises surgeons, oncologists, pathologists and radiologists who review and recommend treatments.

However, in smaller centres or centres with limited resources, MDT is not available. In those clinics, cancer treatment will be relied on the responsible clinician. Delivery of timely and appropriate cancer care could be a challenge. Additionally, clinicians and specialists, with their busy schedule, is impossible to keep abreast of all the new developments in cancer research. With rapid advances in scientific research, this pool of knowledge is expected to continue to burgeon, making keeping up-to-date increasingly onerous.

To address this need, clinicians have adopted the use of Clinical Decision Support Systems (CDSSs) to augment clinical care and decision-making. These are platforms which aim to enhance medical decisions with targeted up-to-date knowledge, patient information, and other health information [3]. Various studies have shown CDSSs to be beneficial in selected settings such as patient safety and diagnosis [4], and to even increase adherence to clinical guidelines [5]. In recent years, advancements in artificial intelligence have also seen its use expand to include CDSSs for oncologic therapy selection, such as IBM's Watson for Oncology (WFO). In a 2018 study, WFO's ability to provide treatment advice for breast cancer was compared against recommendations from a multidisciplinary board, where it showed a high degree of concordance [6]. Since then, several other studies have sought to examine WFO's ability to provide treatment recommendations for cancer such as ovarian [7], gastric [7,8], lung [7,9-10], cervical [11] and colorectal [7] cancers, with mixed results. In particular, both studies which examined the recommendations for gastric cancers showed a much lower concordance rate compared to other cancers [7,8]. One reason for the discordance is that WFO was developed based on patient data and treatment recommendation from experts at Memorial Sloan Kettering Cancer Center, USA. There is significant difference in practice and preference in various geographic regions and individual clinics.

In view of the above, we sought to develop an alternative CDSS for oncologic therapy selection through partnership with Ping An Health Technology, beginning with gastric and oesophageal adenocarcinoma. This would be done with the platform utilizing only major international guidelines from leading authorities such as NCCN, ESMO and JGCA together with high-quality published evidence from high impact medical journals to arrive at case-specific treatment recommendations. In addition, our CDSS system incorporate machine learning which can adapt the preference of individual clinics in different continents. This platform was developed jointly by the specialists from the MDT at National University Health System and National University Cancer Institute, Singapore together with the computing scientists from Ping An Health Technology. We would like to validate this system prospectively at this multicenter clinical trial

by comparing its recommendations with that from the MDT of different tertiary care institutions worldwide.

2. HYPOTHESIS AND OBJECTIVES

2.1. Hypothesis

The recommendations between a specialist-driven multidisciplinary tumour board and an artificial intelligence powered clinical decision support tool would be compared in this study. Its results could potentially improve outcomes for cancer care.

2.2. Primary Objectives

Comparative agreement in recommendations between the two study groups, as measured by concordance rate.

2.3. Secondary Objectives

To identify the reason for the discordance.

2.4. Potential Risks and benefits:

There is minimal risk to our patients as the treatment is still decided by the clinical team as per clinical practice. The comparison is made by our research staffs. The recommendation by Artificial Intelligence Multidisciplinary Tumour Board online platform (AIM online platform) is made available to the clinicians. The clinicians can refer it as an option for their consideration. The risk of the study is related to the data breach during data collection. However, this risk will be minimised by de-identifying using a unique code number and only the study team member will have access to the patient identification.

3. STUDY POPULATION

3.1. List the number of subjects to be enrolled.

We aim to include:

1. Discovery phase: 400 cases (only NUH and NTFGH)
2. Internal retrospective validation phase: 100 cases (only NUH and NTFGH)
3. Prospective validation phase: 1500 cases in a 2 to 3 years

3.2. Population (base)

All patients listed in tumour board with gastric cancer, oesophageal cancer and gastro-oesophageal junction carcinoma.

3.3. Inclusion Criteria

- A. In discovery and internal retrospective validation part:
 - a. Patients with primary gastric adenocarcinoma including preinvasive carcinoma or
 - b. Patients with gastroesophageal junction cancers or

- c. Patients with oesophageal cancer including adenocarcinoma, squamous cell carcinoma and preinvasive carcinoma subtypes.
- B. In prospective validation part:
- a. Patients with primary gastric adenocarcinoma including preinvasive carcinoma or
 - b. Patients with esophageal or gastroesophageal junction adenocarcinoma

3.4. Exclusion Criteria

- A. In discovery and internal retrospective validation part:
- a. Patients with other primary cancers involving the stomach or oesophagus
 - b. Patients with other cancer subtypes
 - c. Patients with concomitant cancers of other organs
- B. In prospective validation part:
- a. Patients with esophageal squamous cell carcinoma
 - b. Patients who participate in clinical trials where the treatment modality is not standard of care

4. TRIAL SCHEDULE

Patients will not undergo any procedures for the study. This is an observational study only. Patients will be treated according to national guidelines. The treatment received by patients may differ per country.

5. STUDY DESIGN

Our study comprises three parts: The Discovery Part (Part 1), The Internal Retrospective Validation Part (Part 2) and The Prospective Validation Part (Part 3).

In the discovery part, de-identified retrospective data on patient and disease characteristics as well as our MDTM recommendations would be collected and utilized to develop the CDSS platform, named AIM online platform, with help from our collaborative partner, Ping An Technology (Shenzhen, China).

In the internal retrospective validation part, additional de-identified retrospective data different from the discovery part will be entered manually into AIM online platform by two trained clinicians, who would be blinded to the treatment recommendations given by the MDTM. These treatment recommendations for each patient would then be collated and compared to the MDTM recommendation. Concordance would be determined by whether the MDTM recommendation is listed in AIM's list of treatment recommendations as a) 1st Recommendation, b) 2nd Recommendation, c) 3rd Recommendation, or d) Not Concordance.

In the external validation part, prospective patient data would be collected over a period of 2 to 3 years from more than 10 different institutions, including centres from Europe, North America and Asia. The prospective data is defined as data collected after 1 May 2020, and the study team will only be collecting data from participants who have given their consent (this may differ per country as per local IRB's requirement). These patient data would be fed into the AIM online

platform within one month of MDTM discussion at these institutions, with clinicians blinded to the generated recommendations. These recommendations would then be immediately compared to the MDTM recommendations to determine concordance. Concordance would be determined by whether the MDTM recommendation is listed in AIM’s list of treatment recommendations as a) 1st Recommendation, b) 2nd Recommendation, c) 3rd Recommendation, or d) Not Concordance. All these data will be captured in the AIM platform.

[figure not shown]
There are 2 stages of validation in the external validation part. In Stage 1, 500 cases will be included from different institutions. The site specific and overall concordance rates will be obtained and analysed. The AIM model will be re-trained to refine the algorithm based on the data collected in stage 1. In Stage 2, 1000 cases will be included from different institutes and site-specific incremental machine learning will be activated. The concordance rate will be obtained and analysed.

At the end of the study, we will also analyse predictive factors for disagreement.

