6. DATA ANALYSIS

6.1. Data Quality Assurance

All the data will be obtained from the tumour board list. The investigator will ensure the data entries are accurate and correct.

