6.2. Data Entry and Storage

All the data will be handled confidentially and anonymously.

In part 1 and 2, the data will be entered into a password encrypted excel sheet and de-identified by a central third party. The individual-identifiers will be kept by the central third party.

In part 3, the anonymous data will be fed into the AIM online platform directly. Only registered user can feed the data into the AIM online platform. A subject identification code will be assigned to each patient and the subject code list is kept within the institution. Ping An team will be responsible for extracting the data for concordance analysis.

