Appendix 1: Example of AIM Platform

 **Clinical Information**

Label

* Age * Gender * Diagnosis

General Information

* Type of Case? New Case Case after Primary Treatment Recurrence

* Primary Treatment?

Endoscopic resection Surgery Neoadjuvant Chemotherapy or Chemoradiation

Chemoradiation, Systemic therapy or Best supportive care

* Tumor classification? (M) M0 M1

* Tumor classification? (T)

Tis T1a T1b T2 T3 T4 T4a T4b

* Tumor classification? (N) N0 N1 N2 N3 N3a N3b

Further Information

Type of Resection? R0 R1 R2

* Have Received Neoadjuvant Chemotherapy or Chemoradiation?

Neoadjuvant Chemotherapy Neoadjuvant Chemoradiation None

Type of lymph node dissection? D1 D2

Figure 1. AIM Online Platform for Gastric Carcinoma

Clinical Information

Label

* Age * Gender * Diagnosis

General Information

* Histologic Classification? Squamous cell carcinoma Adenocarcinoma

Type of GEJ? Stewart Type 1 Stewart Type 2 Stewart Type 3 Unspecified

* Type of Case? New Case Case after Primary Treatment Recurrence

* Tumor classification? (M) M0 M1

* Tumor classification? (T)

Tis T1a T1b T2 T3 T4 T4a T4b

* Tumor classification? (N) N0 N1 N2 N3 N3a N3b

Further Information

ECOG? 0-2 ≥3

Serum creatinine? Normal Abnormally High

Medically fit for surgery? Yes No

Surgically resectable? Yes No

Bulky N? Yes No

The presence of complications? (Bleeding, obstruction, or perforation) Yes No

Figure 2. AIM Online Platform for GEJ Carcinoma

Treatment Recommendation(s) Switch to browse by guideline ⇌

1st Recommendation
2nd Recommendation
3rd Recommendation

- Surgery (may followed by adjuvant therapy)**
 Supported by JGCA 2018
- Chemoradiation**
 Supported by NCCN 2020
- Systemic therapy**
 Supported by NCCN 2020
- Neoadjuvant chemotherapy**
 Supported by ESMO 2016

Your Treatment Option

Please enter your treatment option

Comment

Please enter your comments

Save

Figure 3. Example of AIM Treatment Recommendations

Clinical Information:  Male | 85 | Gastric cancer | T3N3M0 |

Recommended by Guidelines:

-  **Surgery**
(may followed by adjuvant therapy)
-  **Chemoradiation**
-  **Systemic therapy**
-  **Neoadjuvant chemotherapy**

Other Recommendations 

-  **Chemotherapy**
-  **Radiation**
-  **Neoadjuvant chemoradiation**
-  **Best supportive care**

Guideline(1) Meta-analysis(26) RCT(49)

1. **Japanese: Gastric Cancer Guidelines for treatment (Version 5.2018)**

Recommendation: Standard gastrectomy, D2 (may followed by adjuvant therapy)

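### Part 3 does not carry over the Part 2 rule that hides the board's decision from the person entering AIM's inputs, so concordance may be biased upward by an amount the protocol cannot show and that may be small

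*Protocol*

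**What the plan says.** Section 5 sets a different blinding rule for each validation part.

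- **Part 2 (retrospective).** The two trained clinicians who enter the data are those "who would be blinded to the treatment recommendations given by the MDTM".
- **Part 3 (prospective).** Data go into AIM "within one month of MDTM discussion at these institutions, with clinicians blinded to the generated recommendations". The next sentence reads "These recommendations would then be immediately compared to the MDTM recommendations to determine concordance".

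Other sections bear on who handles the data:

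- Section 6.1: "All the data will be obtained from the tumour board list". It does not say whether that list shows the board's decision.
- Section 6.2: "Only registered user can feed the data into the AIM online platform", and "Ping An team will be responsible for extracting the data for concordance analysis".
- Section 2.4: "The comparison is made by our research staffs". The same section lets clinicians see AIM's recommendation and weigh it as one option.

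Appendix 1, Figure 2 (the example form for gastro-oesophageal junction, GEJ, cases) contains inputs that call for judgement. One is "Medically fit for surgery? Yes No"; the others are resectability, bulky nodes and ECOG band. They carry no asterisk, whereas case type, histology and T, N and M do. The example gastric form (Figure 1) shows none of these judgement fields.

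**The concern.** The two rules protect different things. The Part 2 rule protects AIM's inputs from the board's decision. The Part 3 rule, on any reading of who the clinicians are, protects only against AIM's output being seen.

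If the enterer knows that the board chose or declined surgery, a borderline answer on fitness or resectability can drift towards that decision without any intent. AIM may then return the board's answer because its input was shaped by that answer. Part 3 is the prospective test of the primary objective, and an error of this kind is systematic, so more cases do not remove it. Because section 5 grades a match as 1st, 2nd or 3rd recommendation, shaped inputs could also raise the rank of a match that would have occurred anyway.

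**Working it through.** **Step 1: does another control close the gap?**

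| Control | Section | Hides the decision from the enterer? |
|---|---|---|
| Clinicians blinded to AIM's output | 5 | No; it concerns the other side of the comparison |
| Entry limited to registered users | 6.2 | No; it limits access, not knowledge |
| Data taken from the tumour board list | 6.1 | Not stated |
| Comparison by research staff | 2.4 | No; it follows coding |
| Extraction by the technology partner | 6.2 | No; it follows coding |

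Entry after the meeting is the natural reading, because AIM's output is compared at once with a recommendation that must already exist. It remains an inference: the text sets a one-month window and does not say that entry comes after the meeting.

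**Step 2: inputs for a sense of scale.** From the protocol: Stage 1 has n = 500 and Stage 2 has n = 1000 (section 5). Their sum, 1500, agrees with section 3.1. Assumed, because the protocol gives no value:

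- true concordance c = 0.80;
- g, the fraction of discordant cases entered on a form with judgement fields;
- q, the share of those cases that flip to concordant;
- for clustering, 11 equal sites (section 5.1 says more than 10) and an intraclass correlation (ICC) of 0, 0.01 or 0.05.

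**Step 3: formulas.**

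- Design effect DE = 1 + (n/11 − 1) × ICC
- Half-width H = 1.96 × √(DE × c(1 − c)/n)
- Bias = (1 − c) × g × q
- Break-even share, at which bias equals H: q = H / [(1 − c) × g]

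**Step 4: no clustering.**

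- Stage 1: H = 1.96 × √(0.16/500) = 3.51 points; 0.0351/0.20 = 17.5% at g = 1.
- Stage 2: H = 1.96 × √(0.16/1000) = 2.48 points; 0.0248/0.20 = 12.4% at g = 1.

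Dividing by g, and repeating with clustering:

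| ICC | DE, Stage 1 / Stage 2 | H in points | g = 1 | g = 0.5 | g = 0.3 |
|---|---|---|---|---|---|
| 0 | 1.000 / 1.000 | 3.51 / 2.48 | 17.5% / 12.4% | 35% / 25% | 58% / 41% |
| 0.01 | 1.445 / 1.899 | 4.21 / 3.42 | 21.1% / 17.1% | 42% / 34% | 70% / 57% |
| 0.05 | 3.223 / 5.495 | 6.29 / 5.81 | 31.5% / 29.1% | 63% / 58% | 105% / 97% |

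A value above 100% means the bias cannot reach the half-width under those assumptions.

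**Step 5: the bias itself.** With c = 0.80, g = 0.5 and q = 10%, the bias is 0.20 × 0.5 × 0.10 = 0.010, or 1 point, which is below either half-width. At an assumed true rate of 70%, with g = 1 and no clustering, the break-even shares are lower: 4.02/30 = 13.4% and 2.84/30 = 9.5%. They too must be divided by g.

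**The case against.** The strongest reply has four parts.

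1. **The wording may differ for a good reason.** In Part 2 the board's decision already existed, so AIM could not influence it. In Part 3 it could, and the protocol blinds against that new threat. This stands as an explanation, and the two rules do not contradict each other. It does not supply the protection that Part 3 lacks.

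2. **The route is narrow.** The judgement fields are visible only on the example GEJ form and lack the asterisk. If the asterisk marks required fields, which is not stated, they are optional. The example output lists surgical and non-surgical options together, and a match at any of three ranks counts, so recoding need not change the result. All of this stands and is why g enters the calculation. One caution is that the example gastric form displays fields for a previously treated case, so it does not establish what a new gastric case is asked.

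3. **Fitness and resectability may be legitimate board findings.** Giving AIM the facts that the board had is accurate input. Asking a blinded enterer to judge them again could create discordance through error. This stands and shapes the fix.

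4. **The sensitivity analysis is confounded by site.** This stands; it can only be descriptive.

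A reader might infer that Part 3 enterers do know the decision, or that the Part 3 rate will be materially inflated. The documents support neither. No section says what the enterer knows, and a figure after the Part 3 text is not shown. A reader might also infer that the Part 2 rule would prevent the bias. It would not if the tumour board list already carries the board's own assessments, because blinded entry would still pass them to AIM.

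**Conclusion.** The gap is real in the visible text: Part 2 protects the inputs from the board's decision, and Part 3 does not say that it does. The expected direction is upward, in concordance or in matched rank, wherever judgement fields are used. The bias may lie below or above sampling error; the narrower the use of those fields and the stronger the clustering by site, the more likely it lies below. The scale figures rest on assumed values for the true rate, g, the ICC and the number of sites, and do not capture shifts in rank. The severity is minor to moderate: a cheap protection that the sponsor already uses in Part 2 is worth extending, but nothing here shows that the primary result would be wrong.

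**What to change.** In section 5, extend the Part 2 rule to Part 3, for example:

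> *AIM inputs are entered from the case information on the tumour board list with the board's recommendation withheld, where possible by an existing team member who does not know it. They are saved before AIM's output is shown, and later corrections are logged. Facts the board had before it, such as documented resectability, are entered as recorded and not re-judged.*

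Then:

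- record for each case whether the enterer knew the decision;
- keep all cases in the primary concordance rate;
- report concordance by that flag as a descriptive sensitivity analysis, noting the confounding by site;
- reconcile section 2.4, which makes AIM's recommendation available to clinicians, with section 5, which blinds clinicians to it.

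The data source in section 6.1 and the one-month window stay as they are.

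**Cost.** One flag per case; a small platform step to save inputs and log corrections; some site logistics, mainly where the list shows the decision; and local IRB approval of the amendment at each site, which section 8.3 requires before implementation. No extra staff are needed. Some sites may not achieve blinded entry for every case, and the flag records this.

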5.1. Summary of Study Design

This is a multinational observational cohort study. The duration of the study will approximately be 3.5 years (4.5 months for part 1, 0.5 months for part 2 and 2 to 3 years for part 3). Part 1 and 2 will be conducted in NUH and NTFGH only. Part 3 will be conducted in more than 10 different institutes, including centres from Europe, North America and Asia.

Overall Study Plan

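### The protocol does not say whether NUH and NTFGH, whose tumour-board recommendations helped build AIM, enter Part 3, and no rule keeps their cases out of the overall external concordance rate

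*Protocol*

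**What the plan says.** Development is confined to two hospitals. Section 3.1 lists "Discovery phase: 400 cases (only NUH and NTFGH" and Section 5.1 repeats "Part 1 and 2 will be conducted in NUH and NTFGH only". Section 5 says of the discovery part that "our MDTM recommendations would be collected and utilized to develop the CDSS platform".

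Part 3 carries no such limit. Section 3.1 gives "Prospective validation phase: 1500 cases in a 2 to 3 years", with no hospital named. Section 5.1 adds "Part 3 will be conducted in more than 10 different institutes, including centres from Europe, North America and Asia". Section 5 introduces this part under a different label: "In the external validation part, prospective patient data would be collected". The population and eligibility criteria (Sections 3.2 to 3.4) do not restrict by hospital.

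Part 3 has two stages. For Stage 1 (500 cases), "The site specific and overall concordance rates will be obtained and analysed". AIM is then re-trained on the Stage 1 data. In Stage 2 (1000 cases), learning specific to each site is switched on, and a single concordance rate is planned. No passage says which sites enter either rate.

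**The concern.** Prospective and external are different properties. A case seen at NUH or NTFGH after 1 May 2020 is prospective, but it is not external to a tool shaped by the same boards' past recommendations.

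The protocol's own reasoning gives the direction of the bias. Section 1 explains part of the low concordance of another decision-support system by its having been built on one centre's data and expert recommendations, and notes that practice differs between regions and clinics. By the same logic, AIM should agree more often with the boards that supplied its development data.

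Concordance is the primary objective (Section 2.2). If development-site cases enter a rate reported as external, readers will take it as evidence about new institutions when part of it is closer to an internal check.

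**Working it through.** **The plan's own figure.** Stage 1 + Stage 2 = 500 + 1000 = 1500, which agrees with Section 3.1. The protocol gives no expected concordance, precision or power, so nothing further can be reproduced.

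**Formula.** Let w be the share of a stage's cases from the two development hospitals, and g the concordance at those hospitals minus the concordance elsewhere. The pooled rate is w × p(dev) + (1 − w) × p(other). Its excess over p(other) is therefore w × g.

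**Inputs.** Section 8.3 ends the study at 100 valid cases per institute. Section 5.1 gives more than 10 institutes, so 11 is the smallest number. The gap g is not in the documents; 5, 10 and 20 points are assumed. The shares below are also scenarios, because the protocol gives none.

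| Scenario | Share w | g = 5 | g = 10 | g = 20 |
|---|---|---|---|---|
| Two of 15 institutes at 100 each (1500/100 = 15) | 200/1500 = 13.3% | 0.7 | 1.3 | 2.7 |
| Two of 11 equal institutes | 2/11 = 18.2% | 0.9 | 1.8 | 3.6 |
| Stage 1, both hospitals already at 100 | 200/500 = 40% | 2.0 | 4.0 | 8.0 |

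Entries are percentage points of excess. The first two rows apply to either stage if the two hospitals hold the same share in it. The third is a high scenario for Stage 1; it is possible because no per-site limit is set for a stage. If g = 0, every entry is zero.

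**Yardstick.** The 95% half-width is 1.96 × √(p(1 − p)/n), treating cases as independent, with p = 0.80 assumed:
- Stage 1, n = 500: 1.96 × √(0.16/500) = 3.5 points
- Stage 2, n = 1000: 1.96 × √(0.16/1000) = 2.5 points

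At a 10-point gap, equal shares give an excess (1.3 to 1.8 points) smaller than either half-width. The 40% scenario gives 4.0 points, larger than the Stage 1 half-width. The excess is systematic, so recruiting more cases with the same site mix would not reduce it.

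**The case against.** The strongest reply is that the concern rests on silence. The protocol never says that NUH or NTFGH supply Part 3 cases. The contrast between an internal and an external part, and the repeated reference to different institutions, can be read as meaning other institutions. The study-plan figure and some pages are missing from the available copy and might list the sites. This stands: a reader might infer that the two hospitals do contribute and that the external rate is therefore inflated, but the documents do not show that. Equally, the visible text attaches its restriction to Parts 1 and 2 only and contains no exclusion for Part 3.

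Second, Section 1 says the platform uses only major guidelines and high-quality published evidence. If that is literally so, the bias shrinks or vanishes. But it conflicts with Section 5, where the recommendations themselves are used in development. Section 1 also describes the platform as built jointly with specialists from the MDT of the developing institution. The two accounts need reconciling.

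Third, the Stage 1 site-specific rates would reveal a development-site effect. That helps, but it leaves the overall figure as it is, and for Stage 2 no site-specific rates are promised.

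Fourth, the choice of sites for a rate might be left to a SAP, which is not shown. That is fair for table layout. Which institutions count as external is a matter of design, and the protocol already uses the label.

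**Conclusion.** The point holds conditionally. The protocol leaves open whether the two development hospitals enter Part 3, and nothing keeps their cases out of a rate reported under the external label. If they contribute, and if their recommendations shaped AIM as Section 5 says, the rate is likely too high.

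The size is not determined by the documents. At an assumed 10-point gap it is about 1.3 points for two of 15 equal sites, and up to 4.0 points in Stage 1 if both hospitals supply 100 cases. It is zero if they do not contribute or if there is no gap.

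Two stronger readings should be avoided. One is to judge the excess against a single rate on 1500 cases: the protocol describes rates by stage, with re-training between them, so the stage half-widths are the relevant scale. The other is to suppose that leaving out NUH and NTFGH makes Stage 2 external. It does not, because any Stage 1 site that continues into Stage 2 has by then supplied training data, and site-specific learning is active.

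**What to change.** In Section 5:

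- State whether NUH and NTFGH contribute cases to Part 3.
- Define the Stage 1 overall external concordance on all sites other than those two, with any of their cases in a separate row labelled development sites, prospective.
- Make the same split in Stage 2, but describe that rate as performance after re-training and site-specific learning, not as external validation.
- Reconcile Section 1 (guidelines and published evidence only) with Section 5 (MDTM recommendations used in development).

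This costs a few sentences, and nothing in precision if the two hospitals do not contribute. If they do, the external rate rests on fewer cases. In the 40% scenario, Stage 1 falls from 500 to 300 cases and the half-width at 80% concordance rises from 3.5 to 4.5 points (1.96 × √(0.16/300)).
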